6.2.2 Dosage Adjustments, Delays, Rules for Withholding or Restarting, Permanent Discontinuation

6.2.2.1 Infusion Interruption Due to Technical/Logistical Reasons

The administration of blinatumomab should not be interrupted, if possible. In case of infusion interruption due to any technical or logistic reason, the interruption should be as short as possible and the infusion continued at the earliest time possible. Every interruption longer than 1 hour should be documented.

If the interruption is longer than 4 hours, re-start of the infusion should be performed in the hospital under the supervision of the investigator. Administration of dexamethasone premedication prior to resumption of blinatumomab infusion after a treatment interruption of more than 4 hours is described in [Section 6.4](#).

The reason for dose change of blinatumomab is to be recorded on each subject's eCRF.

6.2.2.2 Infusion Interruption/Dose Modifications due to Adverse Events

Infusion interruptions and dose modifications of blinatumomab due to adverse events are detailed in [Table 2](#). Infusions will be resumed according to instructions in [Table 2](#) in order to complete the full treatment cycle, excluding the duration of treatment interruption (56 days blinatumomab in cycle 1, 28 days blinatumomab in optional cycle 2).

Table 2. Infusion Interruption/Dose Modifications of Blinatumomab due to Adverse Events

Toxicity	Grade	Instructions for Treatment Interruption and Restart
Cytokine Release Syndrome	3	
 • Interrupt blinatumomab until the event improves to grade ≤ 1 and administer corticosteroids (refer to Table 3) • Restart no less than 72 hours after the initial observation of the grade 3 event at the following dose levels: 
 ○ If event occurred at 112 $\mu\text{g}/\text{day}$, resume at 28 $\mu\text{g}/\text{day}$ ○ If event occurred at 9 or 28 $\mu\text{g}/\text{day}$, resume at 9 $\mu\text{g}/\text{day}$ • Escalate up 1 dose level after 7 days if toxicity does not reoccur. Increase dose stepwise at 7-day intervals to target dose of 112 $\mu\text{g}/\text{day}$ if toxicity does not reoccur. • Permanently discontinue if: 
 ○ Initial grade 3 CRS does not improve to grade ≤ 1 within 7 days, OR ○ Grade 3 CRS reoccurs at the lower dose level within 7 days of reinitiation OR ○ Grade 3 CRS reoccurs at a dose of 9 $\mu\text{g}/\text{day}$ without prior step-dose escalation
	4	
 • Permanently discontinue blinatumomab
Neurologic Events	3	
 • Interrupt blinatumomab until the event improves to grade ≤ 1 and administer corticosteroids (refer to Table 3) • Restart no less than 72 hours after the initial observation of the grade 3 event at the following dose levels: 
 ○ If event occurred at 112 $\mu\text{g}/\text{day}$, resume at 28 $\mu\text{g}/\text{day}$ ○ If event occurred at 28 $\mu\text{g}/\text{day}$, resume at 9 $\mu\text{g}/\text{day}$ • Escalate up 1 dose level after 7 days if toxicity does not reoccur. Increase dose stepwise at 7-day intervals to target dose of 112 $\mu\text{g}/\text{day}$ if toxicity does not reoccur. • Permanently discontinue if: 
 ○ Initial grade 3 neurologic event occurred at 9 $\mu\text{g}/\text{day}$, ○ Initial grade 3 neurologic event does not improve to grade ≤ 1 within 7 days, OR ○ Grade 3 neurologic event reoccurs at the lower dose level within 7 days of re-initiation
	4	
 • Permanently discontinue blinatumomab
	4	
 • Permanently discontinue blinatumomab

Approved

ALP=alkaline phosphatase; ALT=alanine aminotransferase; AST=aspartate aminotransferase; CRS=cytokine release syndrome; INR=international normalized ratio; MRI=magnetic resonance imaging; RUQ=right upper quadrant; TBL=total bilirubin; ULN=upper limit of normal
 * Obtain brain MRI and perform cerebro spinal fluid (CSF) analysis, if there are no contraindications

Table 2. Infusion Interruption/Dose Modifications of Blinatumomab due to Adverse Events

Toxicity	Grade	Instructions for Treatment Interruption and Restart
Seizure*		
 Interrupt blinatumomab, administer corticosteroids (refer to Table 3) and antiseizure medication per local practice For restart, refer to grade 3 neurologic events above for dose level rules for re-instituting infusion Do not re-initiate blinatumomab until 7 days after the last seizure and after therapeutic levels of antiseizure medication are likely to have been achieved Permanently discontinue if a second seizure occurs with re-initiation of blinatumomab at any dose
Elevated liver enzymes		
 Interrupt blinatumomab (refer to Table 4) if any one of the following occurs: 
 TBL > 3x ULN at any time ALP > 8x ULN at any time AST or ALT > 8x ULN at any time AST or ALT > 5x ULN but < 8x ULN for ≥ 2 weeks AST or ALT > 3x ULN with clinical signs or symptoms that are consistent with hepatitis (eg, RUQ abdominal pain/tenderness, fever, nausea, vomiting, jaundice) Permanently discontinue blinatumomab if: 
 TBL > 2x ULN OR INR >1.5 (for subjects not on anticoagulant therapy) 
AND
 
 AST or ALT > 3x ULN (when baseline was <ULN) 
AND
 
 no other cause for the combination of the above laboratory abnormalities is immediately apparent 
Refer to Section 6.5 for additional details

Approved

Page 2 of 3

ALP=alkaline phosphatase; ALT=alanine aminotransferase; AST=aspartate aminotransferase;
 CRS=cytokine release syndrome; INR=international normalized ratio; MRI=magnetic resonance imaging;
 RUQ=right upper quadrant; TBL=total bilirubin; ULN=upper limit of normal
 * Obtain brain MRI and perform cerebro spinal fluid (CSF) analysis, if there are no contraindications

Table 2. Infusion Interruption/Dose Modifications of Blinatumomab due to Adverse Events

Toxicity	Grade	Instructions for Treatment Interruption and Restart
Other clinically relevant adverse events	3	
 • Interrupt blinatumomab until event improves to grade ≤ 1 (refer to Table 2) • Restart no less than 72 hours after the initial observation of the grade 3 event at the following dose levels: 
 ○ If event occurred at 112 $\mu\text{g}/\text{day}$, resume at 28 $\mu\text{g}/\text{day}$ ○ If event occurred at 9 or 28 $\mu\text{g}/\text{day}$, resume at 9 $\mu\text{g}/\text{day}$ • Escalate up 1 dose level after 7 days if toxicity does not reoccur. Increase dose stepwise at 7-day intervals to target dose of 112 $\mu\text{g}/\text{day}$ if toxicity does not reoccur. • Permanently discontinue blinatumomab if: 
 ○ Initial grade 3 event does not improve to grade ≤ 1 within 14 days, OR ○ Grade 3 event reoccurs at the lower dose level within 7 days of re-initiation, OR • Grade 3 event reoccurs at a dose of 9 $\mu\text{g}/\text{day}$ without prior step-dose escalation
	4	
 • Permanently discontinue blinatumomab

Page 3 of 3

ALP=alkaline phosphatase; ALT=alanine aminotransferase; AST=aspartate aminotransferase; CRS=cytokine release syndrome; INR=international normalized ratio; MRI=magnetic resonance imaging; RUQ=right upper quadrant; TBL=total bilirubin; ULN=upper limit of normal

* Obtain brain MRI and perform cerebro spinal fluid (CSF) analysis, if there are no contraindications

6.2.2.3 Permanent Discontinuation

Blinatumomab will be permanently discontinued for:

- **Cytokine Release Syndrome**
 - Initial grade 3 cytokine release syndrome (CRS) **that** does not improve to grade ≤ 1 within 7 days
 - Grade 3 CRS that reoccurs at the lower dose level within 7 days of reinitiation
 - Reoccurs at a dose of 9 $\mu\text{g}/\text{day}$
 - Grade 4 CRS.
- **Neurologic Event**
 - Initial grade 3 neurologic event occurred at 9 $\mu\text{g}/\text{day}$
 - Initial grade 3 neurologic event does not improve to grade ≤ 1 within 7 days
 - Grade 3 neurologic event reoccurs at the lower dose level within 7 days of reinitiation
 - Reoccurs at a dose of 9 $\mu\text{g}/\text{day}$
 - Grade 4 neurologic event
 - A second seizure that occurs after reinitiation of blinatumomab.

Approved

- Elevated liver enzymes
 - TBL > 2x ULN OR INR >1.5 (for subjects not on anticoagulant therapy)
AND
 - AST/ALT > 3x ULN (when baseline was <ULN)
AND
 - no other cause for the combination of the above laboratory abnormalities is immediately apparent
- Other clinically relevant adverse events
 - Initial grade 3 event does not improve to grade \leq 1 within 14 days (with the exception of delay in restart due to logistical difficulties, in which case the restart may be postponed for an additional 7 days).
 - Grade 3 event reoccurs at the lower dose level within 7 days of reinitiation
 - Reoccurs at a dose of 9 μ g/day

Subjects who discontinue blinatumomab for protocol defined reasons may be offered alternative standard of care chemotherapy at the discretion of the treating physician. Subjects shall be followed for survival endpoints.

Subjects who permanently discontinue study medication due to adverse event should continue with other study procedures, including response assessment, as appropriate.

6.3 Non-Amgen Non-investigational Product IC Chemotherapy

Non-Amgen non-IP IC chemotherapy will also be used in this study.

Subjects randomized to the IC arm will receive no more than 3 cycles (maximum cycle length 28 days) of S2 chemotherapy prior to response assessment. Assessment of response shall be completed no later than at the end of the third cycle of chemotherapy.

6.3.1 Recommended Regimens for IC S2 Chemotherapy

- R-ICE ([Gisselbrecht et al. 2010](#); [Kewalramani et al. 2004](#); [Moskowitz et al. 1999](#))
- R-DHAP ([Gisselbrecht et al. 2010](#); [Mey et al. 2006](#); [Velasquez et al. 1988](#))
- R-GDP ([Crump et al. 2004](#); [Crump et al. 2014](#))
- R-ESHAP ([Martin et al. 2008](#); [Velasquez et al. 1994](#))
- R-EPOCH ([Gutierrez et al. 2000](#))

Regimens not listed are permitted with the exception of those with any of the characteristics described in [Section 6.3.2](#).

Dose adjustment, cycle delays, and supportive care for IC chemotherapy are per institutional standards. The reason for dose change of IC chemotherapy is to be

recorded on each subject's eCRF. Regimen, planned doses, intended cycle length, reason for dose reduction, and reason for cycle delays will be recorded.

The dose, start date/time, stop date/time, frequency of IC chemotherapy, dose reduction, dose interruption, and cycle delay are to be recorded on each subjects eCRF.

6.3.2 Prohibited Regimens for IC S2 Chemotherapy

- Radioimmunoconjugates such as (but not limited to) ⁹⁰Y ibritumomab tiuxetan and ¹³¹I tositumomab are prohibited.
- Regimens with planned cycle durations of greater than 28 days are prohibited.
- Regimens that include "maintenance" treatment that extends beyond the cycle duration are prohibited.
- Regimens that include alternating cycles of non-identical chemotherapies are prohibited.

6.3.3 Regimens That are Permitted but Discouraged for Transplant Eligible Subjects

Regimens that include fludarabine or melphalan (eg, mini-BEAM) are strongly discouraged due to the adverse impact on HSC mobilization.

6.4 Other Protocol-required Therapies

All other protocol-required therapies, including dexamethasone, that are commercially available are not provided or reimbursed by Amgen (except if required by local regulation). The investigator will be responsible for obtaining supplies of these protocol-required therapies. Additional details regarding these protocol-required therapies are provided in the IPIM.

Dexamethasone Premedication

Premedication with dexamethasone is required before each blinatumomab treatment cycle for the prevention prophylaxis of CRS. Dexamethasone premedication prior to resumption of blinatumomab infusion after a treatment interruption of < 4 hours is described in [Table 3](#).

Approved

Table 3. Dexamethasone Predose Treatment and for Events

Treatment Phase	Target Subjects	Dexamethasone Dose
Predose dexamethasone prior to each blinatumomab treatment cycle and before each dose step increase	All subjects	Dexamethasone 20 mg IV: within 1 hour prior to start of treatment in each treatment cycle, and within 1 hour prior to dose step (increase).
Infusion interruption/dose modification due to adverse event or interruption due to technical/logistical event	Subjects who interrupt treatment > 4 hours	Dexamethasone 20 mg IV: within 1 hour prior to re-start of treatment
In case of signs of cytokine release syndrome	Subjects with signs of cytokine release syndrome	Dexamethasone orally or IV at a dose maximum of 3 doses of 8 mg (24 mg/day) for up to 3 days. The dose should then be reduced step-wise over 4 days.
Infusion Interruption/Dose Modification Due to Neurologic Events	Subjects with neurologic event ^a	Dexamethasone should be administered at a dose of at least 24 mg/day for up to 3 days. Dexamethasone will then be reduced step-wise over 4 days.

IV = intravenous

^a As outlined in [Section 6.2.2.2](#).

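### Section 6.4 ties dexamethasone before a restart to interruptions under 4 hours, while Table 3 and Section 6.2.2.1 tie it to interruptions over 4 hours; the three places must be reconciled

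*Protocol*

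**What the plan says.** Three places in the protocol form a chain on this point.

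- **Section 6.2.2.1** deals with interruptions for technical or logistical reasons. It states that "dexamethasone premedication prior to resumption of blinatumomab infusion after a treatment interruption of more than 4 hours is described in" Section 6.4. It uses the same limit for where the infusion may be resumed: "If the interruption is longer than 4 hours, re-start of the infusion should be performed in the hospital".
- **Section 6.4, text**, makes dexamethasone mandatory before each cycle as CRS prophylaxis and then adds: "Dexamethasone premedication prior to resumption of blinatumomab infusion after a treatment interruption of < 4 hours is described in" Table 3.
- **Section 6.4, Table 3**, has one row on dosing before a restart. It covers interruptions from adverse events and from technical or logistical causes, and its target group is "Subjects who interrupt treatment > 4 hours". The dose and timing are given in that row. The other rows cover the start of a cycle or a dose step, signs of CRS, and neurologic events. None sets a rule for interruptions shorter than 4 hours.

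The SAP does not address dexamethasone premedication.

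**The concern.** The sentence in Section 6.4 is the middle link of the chain. It gives the opposite side of the 4-hour limit from the section that refers to it and from the table it refers to. It is not background text: it sits under protocol-required therapies and concerns a mandatory preventive measure.

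The situation it governs is foreseen. Infusion may continue at home with bag changes (Section 6.2.1.2), Section 6.2.2.1 asks for every interruption longer than 1 hour to be documented, and Table 2 builds interruption and restart into the handling of toxicity. At stake is whether sites apply one rule when they resume the infusion, and whether a past restart can be judged compliant or a deviation against a single standard.

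**Working it through.** No arithmetic applies. The claim rests on no sample size, event count or error rate, and the plan states no figure to reproduce. The check is to set the linked places side by side.

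| Place in protocol | Interruption length tied to premedication | Where it sends the reader |
|---|---|---|
| Section 6.2.2.1 | more than 4 hours | Section 6.4 |
| Section 6.4, text | less than 4 hours | Table 3 |
| Table 3, restart row | more than 4 hours | (end of chain) |

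**Step 1: follow the chain for an interruption under 4 hours.** Section 6.2.2.1 attaches no premedication to it. The Section 6.4 text says the instruction is in Table 3. Table 3 contains none. The sentence points to something that is not there.

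**Step 2: follow it for a technical or logistical interruption over 4 hours.** Section 6.2.2.1 sends the reader to Section 6.4. The Section 6.4 text does not mention this length. Table 3 does, with dose and timing.

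**Step 3: follow it for an adverse-event interruption.** Table 2 allows a restart no sooner than 72 hours after a grade 3 CRS, neurologic or other clinically relevant event is first observed, and no sooner than 7 days after the last seizure. If the infusion is stopped promptly when the event is seen, these interruptions are far longer than 4 hours. Table 3 includes them by name. The Section 6.4 sentence, read literally, does not.

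**Step 4: check that the text is current.** The Amendment 2 list of changes itemises neither Section 6.2.2.1, nor Section 6.4, nor Table 3. The disagreement is within the current protocol, not between current and superseded wording.

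**Step 5: check for a conversion error.** Both inequality signs appear within Section 6.4, a short distance apart, so a systematic swap of signs is unlikely. A single misread sign cannot be fully excluded, but nothing in the text suggests one.

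**The case against.** The best reply is that the Section 6.4 sentence only points elsewhere. It carries no dose, timing or target group; all of these are in Table 3, in the same section. A site cannot act on the sentence alone, and on opening the table it meets the other threshold. This stands. A reader might infer that sites would premedicate exactly the opposite set of restarts, but that would require taking the dose from a table row while ignoring the target group in the same row. A query or uneven practice is plausible; systematic reversal is not shown.

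Scope is also limited. A reader might infer that every restart is in doubt. Dexamethasone at the start of each cycle and before each dose increase has its own row for all subjects and is untouched. Adverse-event restarts are named in Table 3, so although the literal texts disagree there too, the practical ambiguity lies mainly with technical or logistical interruptions. The documents give no count of these.

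A reader might further infer that uneven steroid use would disturb the response or cytokine results. The documents do not support that. The response scan follows a 14-day treatment-free interval. Cytokines are exploratory, and most samples are timed around the start of infusion and the dose steps, where dexamethasone is already required for everyone. No figure for any effect is available.

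Two places against one also makes it tempting to call the Section 6.4 sign a slip and name the correct rule. Agreement between two places does not settle a clinical rule; that is for the sponsor.

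Finally, Section 6.4 says the Investigational Product Instruction Manual holds further detail on these therapies. It is not among the documents, so what sites were told in practice is unknown. It could not remove a contradiction inside the protocol.

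**Conclusion.** The contradiction is confirmed. Section 6.2.2.1 and Table 3 place premedication on the longer side of 4 hours; the Section 6.4 text, which links them, places it on the shorter side and refers to a rule that Table 3 does not contain. The size is one sentence in conflict with two linked places, in an instruction on required CRS prophylaxis. The consequence that can be supported is possible confusion or inconsistent premedication across sites when an interrupted infusion is resumed.

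The response endpoint, sample size, power and alpha are unaffected. The conclusion assumes only that the inequality sign in Section 6.4 was read correctly from the PDF. If phase 2 treatment has ended and phase 3 does not start, the safety gain for future restarts falls away, and the remaining value is a single standard for classifying past ones.

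**What to change.** The sponsor should decide the intended rule and reconcile the Section 6.4 text, Table 3 and Section 6.2.2.1 so that all three state the same interruption length. The manual should be checked against the result, and sites should receive a short clarification. No threshold is proposed here.

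The cost is a minor text edit and a site notice. No analysis, sample size or schedule of assessments changes.

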6.5 Hepatotoxicity Stopping and Rechallenge Rules

Subjects with abnormal hepatic laboratory values (ie, alkaline phosphatase [ALP], AST, ALT, TBL) and/or international normalized ratio [INR] and/or signs/symptoms of hepatitis (as described below) may meet the criteria for withholding or permanent discontinuation of Amgen IP or other protocol-required therapies as specified in the Guidance for Industry Drug-Induced Liver Injury: Premarketing Clinical Evaluation, July 2009).

6.5.1 Criteria for Withholding and/or Permanent Discontinuation of Amgen Investigational Product and Other Protocol-required Therapies due to Potential Hepatotoxicity

The following stopping and/or withholding rules apply to subjects for whom another cause of their changes in liver biomarkers (TBL, INR and transaminases) has not been identified.

Approved

Important alternative causes for elevated AST/ALT and/or TBL values include, but are not limited to:

- Hepatobiliary tract disease
- Viral hepatitis (eg, Hepatitis A/B/C/D/E, Epstein-Barr Virus, cytomegalovirus, Herpes Simplex Virus, Varicella, toxoplasmosis, and Parvovirus)
- Right sided heart failure, hypotension or any cause of hypoxia to the liver causing ischemia.
- Exposure to hepatotoxic agents/drugs or hepatotoxins, including herbal and dietary supplements, plants and mushrooms
- Heritable disorders causing impaired glucuronidation (eg, Gilbert's Syndrome, Crigler-Najjar syndrome) and drugs that inhibit bilirubin glucuronidation (eg, indinavir, atazanavir)
- Alpha-one antitrypsin deficiency
- Alcoholic hepatitis
- Autoimmune hepatitis
- Wilson's disease and hemochromatosis
- Nonalcoholic Fatty Liver Disease including Steatohepatitis
- Non-hepatic causes (eg, rhabdomyolysis, hemolysis)
- Cytokine storm

If IP is withheld, the subject is to be followed according to recommendations in [Appendix A](#) for possible drug induced liver injury (DILI).

Rechallenge may be considered if an alternative cause for impaired liver tests (ALT, AST, ALP) and/or elevated TBL, is discovered and the laboratory abnormalities resolve to normal or baseline ([Section 6.5.2](#)).

Approved

Table 4. Conditions for Withholding and/or Permanent Discontinuation of Amgen Investigational Product and Other Protocol-required Therapies due to Potential Hepatotoxicity

Analyte	Temporary Withholding	Permanent Discontinuation
TBL	> 3x upper limit of normal (ULN) at any time	> 2x ULN
INR	--	> 1.5 (for subjects not on anticoagulation therapy)
AST/ALT	> 8x ULN at any time > 5x ULN but < 8x ULN for ≥ 2 weeks > 5x ULN but < 8x ULN and unable to adhere to enhanced monitoring schedule > 3x ULN with clinical signs or symptoms that are consistent with hepatitis (such as right upper quadrant pain/tenderness, fever, nausea, vomiting, jaundice).	In the presence of no important alternative causes for elevated AST/ALT and/or TBL values > 3x ULN (when baseline was < ULN)
ALP	> 8x ULN at any time	--

ALP = alkaline phosphatase; ALT = alanine aminotransferase; AST = aspartate aminotransferase; TBL = total bilirubin.

Approved

6.5.2 Criteria for Rechallenge of Amgen Investigational Product and Other Protocol-required Therapies After Potential Hepatotoxicity

The decision to rechallenge the subject should be discussed and agreed upon unanimously by the subject, investigator, and Amgen.

If signs or symptoms recur with rechallenge, then Amgen IP and other protocol-required therapies, as appropriate should be permanently discontinued. Subjects who clearly meet the criteria for permanent discontinuation (as described in [Table 4](#)) should never be rechallenged with blinatumomab.

6.6 Concomitant Therapy

Throughout the study, investigators may prescribe any concomitant medications or treatments deemed necessary to provide adequate supportive care except for those listed in [Section 6.9](#).

All treatments that the investigator considers necessary for a subject's welfare may be administered at the discretion of the investigator in keeping with the community standards of medical care.

All concomitant medication will be recorded on the eCRF including all prescription, over-the-counter, herbal supplements, and IV medications and fluids.

Concomitant therapies are to be collected from signing of the consent form through the safety follow-up period. Following the safety follow-up period, only medications taken for the treatment of NHL, including agents used for transplant conditioning, will be collected. Following the safety follow-up period, radiation administered will also be captured on a designated eCRF.

The following should be recorded: medication name, indication, dose, route, frequency, start date, and stop date. If changes occur during the study period, documentation of drug dosage, frequency, route, and date may also be included on the eCRF.

